reduction is permitted if clinically indicated.

In the expansion portion (Stage 2), 20 patients will be randomized in a 1:1 ratio to receive GDC-0084 either under fasted or fed conditions.

Statistical Analysis

Analysis Populations:

- The Intent -to-Treat (ITT) population includes all randomized patients; ITT analyses will be conducted on the basis of the arm assigned at randomization
- The Modified Intent-to-Treat (mITT) population includes all eligible patients who received at least 1 dose of GDC-0084 and have evaluable post-baseline tumor response data;
- Safety population (SAF): All eligible patients who received at least 1 dose of GDC-0084 will be included in the safety population. Safety analyses will be conducted on the basis of initial received treatment;
- PK population: All eligible patients in the safety population who have an adequate concentration vs. time profile to determine PK parameters;
- A Per-Protocol (PP) subset will also be used to analyze endpoints of clinical benefit and will be based on study drug exposure (compliance and/or time on study drug) and major protocol deviations. The criteria for inclusion in the PP subset will be finalized and documented prior to database lock.

Timing of Analyses:

Regular cohort safety reviews will be performed as described above during Stage 1 to support dose-escalation and if necessary, de-escalation decisions.

After all patients in Stage 2 have completed one cycle of treatment or discontinued treatment, an interim analysis of safety, PK, FDG-PET and select clinical benefit endpoints will be evaluated.

A final analysis will be performed when all patients discontinue treatment and complete their End of Treatment visit. Supplemental analyses may be performed at the completion of the study but will be considered exploratory.

General Considerations:

Data from Stage 1 and Stage 2 may be summarized separately. For Stage 1 assessment, summaries will be presented by dose level and overall. For Stage 2, summaries will be presented by treatment arm (fed versus fasting) and overall. Selected safety parameters may be summarized using pooled data from the selected dose level in Stage 1 and fasted patients in Stage 2.

There may be a statistical comparison of C_{max}/AUC between fasted and fed patient data in stage 2.

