- Mucositis/stomatitis Grade 3 not responding to standard-of-care therapy or Grade 4. Sites should consider using an alcohol-free dexamethasone 0.5 mg per 5mL oral solution (elixir) if such symptoms eventuate. Patients may be instructed to use 10ml oral solution swished for up to two minutes and then spit, up to four times daily (Rugo et al. 2017).
- Decrease in left ventricular ejection fraction (LVEF) to ≤ 45%;
- Increase of QTc to ≥ 500 msec or by 60 msec:
- Pneumonitis Grade ≥ 2.

After determination of the MTD, patients continue to receive their protocol assigned dose levels of GDC-0084 until progression of their disease or an unacceptable toxicity, whichever occurs first.

Patients who experience disease progression or an unacceptable toxicity at any time during the study, or, in their opinion or the opinion of the Investigator, are not benefiting from GDC-0084, will be discontinued from study treatment. Under certain circumstances in which an AE (or DLT) is reversible and the risk/benefit assessment suggests a reasonable rationale for continued administration of study drug, patients may continue with agreement from the Investigator and the medical monitor. This may include dose reduction and change of treatment schedule. An End of Treatment visit will be performed approximately 28 days after the last dose of GDC-0084.

3.7.2 Stage 2

Stage 2 of the study will be a two-arm, randomized, open-label expansion cohort to further characterize safety, tolerability and PK of GDC-0084 when administered QD in 28-day cycles, and to explore the effect of food on the PK of GDC-0084, as well as to provide a preliminary assessment of single-agent activity of GDC-0084 in patients with GBM.

The expansion will start with a screening period, followed by treatment and follow-up periods. It will be initiated with recruitment of new patients as soon as the MTD for QD dosing has been determined.

Approximately 20 patients will be enrolled in the expansion cohort according to the defined study eligibility criteria, to perform the comparison of safety and clinical activity. On Days 1 and C2D1, 10 patients will receive GDC-0084 in a fed state, while the remaining 10 patients will receive GDC-0084 in a fasted state. Patients will be allocated to either fed or fasted arms via a central randomization mechanism.

Patients enrolled in Stage 2 may continue the study at the dose allocated until disease progression or unacceptable toxicity.

Version: Amendment 4 Date: 31 Mar 2020

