Fasted Arm	On Days C1D1 and C2D1, those patients allocated to the fasted arm should have fasted overnight for at least 10 hours, and should continue to fast for at least 4 hours post-dose. Water may be consumed as required, except for the period one hour before dosing to one hour post-dosing.	As above.

4.4.2 **Schedule of Assessments**

Screening evaluations are to be conducted within 28 days prior to start of protocol-directed therapy. Scans must be done within 14 days prior to the start of therapy. If the patient's condition is deteriorating during the 28-day screening period, laboratory evaluations should be repeated within 24 hours prior to initiation of the first cycle of therapy. Timing of assessments is given in Table 1 below. Details of assessments are outlined in Section 4.6.

Sponsor: Kazia Therapeutics Limited Version: Amendment 4 Date: 31 Mar 2020

Protocol Number: NVGN-0084-201

IND Number: 112,608

Table 1: Schedule of Assessments – Stage 1 and Stage 2

	Screening Day -28 to -1	Cycle 1 Enrollment / Week 1 Day 1	Cycle 2 Day 1	Repeat Cycle 2 Assessments for Cycle 3 and onwards			[
				Every 4 Weeks	Every 8 Weeks	End of Treatment Visit	Short-Term Follow-up Visit	Long term Follow-up Visits ^k
Visit Window			+/- 3 days	+/- 3 days	+/- 3 days	Within 7 days	28 days from last dose +/- 3 days	+/- 14 days
Informed Consent	Х							
MGMT Promoter Status ^a	Х							
Demographics	Х							
Medical/Cancer History	Х							
Physical Examination	Х	Х	Х	Х		Х	Х	
Ophthalmologic Examination ^b	Х				Х			
Urine Test for protein ^c	Х							
Vital Signs	Х	Х	Х	Х		Х	Х	
Weight	Х	Х	Х	Х		Х	Х	
Height	Х							
KPS	Х	Х	Х	Х		Х	Х	
MRI ^d		Х			Х	Х		
FDG-PET scane		Х			Ī			
ECG ^f	Х	Х	Х	Х		Х	Х	
LVEF (ECHO or MUGA)	Х				Х			

Version: Amendment 4 Date: 31 Mar 2020 Protocol Number: NVGN-0084-201

IND Number: 112.608

		Cycle 1	Cycle 2		Cycle 2 ts for Cycle nwards			
	Screening Day -28 to -1	Enrollment / Week 1 Day 1	Day 1	Every 4 Weeks	Every 8 Weeks	End of Treatment Visit	Short-Term Follow-up Visit	Long term Follow-up Visits ^k
Visit Window			+/- 3 days	+/- 3 days	+/- 3 days	Within 7 days	28 days from last dose +/- 3 days	+/- 14 days
aPTT/PT/INR	Х	Х	Х	Х		Х		
bHCG Pregnancy Test ^g	Х	Х	Х	Х		Х		
PK Sampling ^h		Х	Х					
Hematology, Chemistryi	Х	Х	Х	Х		Х	Х	
GDC-0084 Administration ^j		Х	Х	Х				
Study Drug Compliance			Х	Х		Х		
Concomitant Medications/Procedures	Х	Х	Х	Х		Х	Х	
AEs	Х	Х	Х	Х		Х	Х	
Disease status (including PFS and OS)								Х
Disease related therapies								Х

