4.6.12 Follow-up Visits

There is a short-term follow-up visit 28 days after end of study treatment (last dose). There is longterm follow-up performed by telephone conversation or site visit (depending on practical considerations) where all patients in Stage 1 and Stage 2 who discontinue study treatment will be followed every 8 weeks until determination of progressive disease (PD) and then until death unless the patient requests to be withdrawn from survival follow-up or termination of the study by the Sponsor. This request must be documented in the source documents and signed by the Investigator.

Duration of Therapy

After the screening period of up to 28 days, patients start to take GDC-0084 in 28-day cycles (every day continuous dosing is intent). Dose and regimen depend on the study stage and findings during the study (see Section 3.7 and Section 4.4.1).

In the absence of treatment delays due to AEs, treatment may continue until 1 of the following criteria applies:

- DLTs (Stage 1, Cycle 1);
- Disease progression;
- Intercurrent illness that prevents further administration of treatment:

Version: Amendment 4 Date: 31 Mar 2020

IND Number: 112.608

- Patient decides to withdraw from the study;
- General or specific changes in the patient's condition that render the patient unacceptable for further treatment in the judgment of the Investigator.

Protocol Number: NVGN-0084-201

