6.3.2 Timing of Analyses

Regular cohort safety reviews will be performed as described above during Stage 1 to support dose-escalation and if necessary, de-escalation decisions.

A final analysis will be performed when all patients discontinue treatment and complete their EoT visit. Supplemental analyses may be performed at the completion of the study but will be considered exploratory.

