6.3.3 General Considerations

Data from Stage 1 and Stage 2 may be summarized separately. For Stage 1 assessment, summaries will be presented by dose level and overall. For Stage 2, summaries will be presented by treatment arm (fed versus fasting) and overall. Selected safety parameters may be summarized using pooled data from the selected dose level in Stage 1 and fasted patients in Stage 2.

Version: Amendment 4 Date: 31 Mar 2020

Protocol Number: NVGN-0084-201

IND Number: 112,608

There may be a statistical comparison of C_{max}/AUC between fasted and fed patient data in Stage 2. Descriptive statistics (N, mean, standard deviation, median, minimum, and maximum) will be presented for continuous variables. Geometric means and geometric coefficient of variation will also be presented for PK data. Frequency distributions (counts and associated percentages) will be presented for categorical variables. Median, 25th and 75th percentiles and confidence intervals (CIs) will be presented for time-to-event data. Unless specified otherwise, CIs will be presented as 95%

The study is descriptive in nature and is not powered for a confirmatory statistical goal or objective. However, comparisons of treatment arms may be performed in Stage 2. Formal hypothesis testing will not be done, and no adjustment for multiple comparisons will be used.

Individual patient data listings will be provided to support summary tables.

The effects of noncompliance, treatment discontinuations, premature study withdrawals, subsequent therapies, and covariates will be assessed to determine the impact on the general applicability of results from this study.

6.3.4 **Analysis of Clinical Benefit**

Analyses of tumor-related endpoints will include all evaluable data collected until initiation of subsequent anti-cancer therapy. Sensitivity analyses may be performed excluding data collected after the End of Treatment Visit.

Requirements for PD confirmation and any impact on the calculations for analysis (i.e., PFS, TTP. duration or stable disease, etc.) and associated sensitivity analyses will be described in the SAP.

For Stage 2 tumor-related endpoints, the responses assigned by the blinded central review will be used as the primary measure for analysis, and the responses assigned by the Investigator will be used as supportive measures for analysis.

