The exploratory endpoint DCR is defined as the proportion of patients achieving a confirmed BOR of CR, PR or SD according to a) RANO criteria and b) modified RANO criteria. BOR is defined as the best response recorded from first dose (Stage 1) or randomization (Stage 2) until progressive disease , death, withdrawal of consent or end of study, whichever occurs first. To be assigned a status of CR, PR or SD, the response must be confirmed by repeat assessments that should be performed no less than 28 days after the criteria for response are first met, i.e., patients need to have two consecutive assessments of CR, PR or SD. To be assigned a BOR of SD patients must have a minimum duration of SD of at least 6 weeks.

The number and proportion of responders and non-responders based on objective response rate and DCR will be presented with 95% Clopper-Pearson Cls. Further, objective response rate and DCR will be compared between treatment arms using Fisher's exact test. The difference in the proportion of responders and corresponding 95% CI (based on the Hauck-Anderson approach) will also be displayed.

Analyses of PFS will be repeated using modified RANO criteria.

Additional exploratory analyses of the data will be conducted as deemed appropriate.

6.3.5 **Safety Analysis**

All safety analyses will be conducted in the safety population.

AEs will be coded according to the Medical Dictionary for Regulatory Activities (MedDRA). The severity of AEs will be graded according to the United States NCI CTCAE, version 4.03.

TEAEs are defined as any AE occurring or worsening on/after the first study drug dose and within 28 days after the last dose date. TEAEs leading to study drug discontinuation, TEAEs leading to dose reduction/interruption, TEAEs related to study drug, SAEs, TEAEs leading to study drug discontinuation, and TEAEs with an outcome of death will be summarized by system organ class, and preferred term. Disease progression and death will be reported as part of the study endpoints and not as AEs or SAEs. A summary of TEAEs of NCI CTCAE Grade 3 or higher, as well as the most frequent TEAEs (preferred terms) by grade, and TEAEs by relationship to study treatment, will be provided. Additionally, a summary will be done for AEs using the worst grade of the event.

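### The End of Treatment visit has two conflicting timings and triggers the final analysis, which can therefore begin before the 28-day adverse event window has closed for the last patients to stop

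*Combined protocol and SAP*

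**What the plan says.** **Visit timing.** Section 3.7.1 closes its Stage 1 text with: "An End of Treatment visit will be performed approximately 28 days after the last dose of GDC-0084". Table 1 in section 4.4.2, titled for both stages, has separate columns for two visits. The End of Treatment (EoT) visit has a 7-day window and no date to count from. The Short-Term Follow-up Visit is set at "28 days from last dose +/- 3 days". The synopsis and sections 4.6.12 and 4.8 also attach the 28-day visit to short-term follow-up, not to EoT.

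**Analysis trigger.** Section 6.3.2 reads: "A final analysis will be performed when all patients discontinue treatment and complete their EoT visit". The synopsis has the same rule. Section 6.3.2 then says of anything later: "Supplemental analyses may be performed at the completion of the study but will be considered exploratory".

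**Safety window.** Section 6.3.5 counts an adverse event as treatment-emergent (a TEAE) if it starts or worsens from first dose and "within 28 days after the last dose date". The synopsis agrees, section 5.2 runs adverse event reporting for the same 28 days, and section 6.3.5 uses that cut for concomitant medications.

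**The concern.** One visit name carries two timings, and the start of the final analysis hangs on it. If EoT is about four weeks after the last dose, the trigger and the safety window close together. If EoT is the early visit in Table 1, the trigger can be met while the last patients to stop are still inside the period in which the plan counts their adverse events.

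The final safety tables could then miss late TEAEs, SAEs and concomitant medications in those patients. When the data arrived, the only place the protocol gives them is a supplemental analysis that it calls exploratory. Safety and tolerability is the primary objective, so the main safety report should cover the whole window that the plan defines.

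**Working it through.** The plan states no figure to reproduce. The check is a day count, with day 0 as the last dose.

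**Inputs**
- EoT in section 3.7.1: about day 28.
- EoT in Table 1: a 7-day window, anchor not stated.
- Short-Term Follow-up Visit in Table 1: 28 ± 3, so day 25 to day 31.
- End of the TEAE window (synopsis, 6.3.5) and of adverse event reporting (5.2): day 28.
- Longest delay between cycles before a patient is removed (4.9.1): 2 weeks, or 14 days.

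**Step 1: size of the conflict.** With both timings counted from last dose, the two sections differ by at least 28 − 7 = 21 days on the same visit, and by up to 28 − 0 = 28 days.

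**Step 2: open window when the trigger is met.** For the last patient to stop, open days = 28 − day of EoT.

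| Reading of EoT timing | Day of EoT | Days still open |
|---|---|---|
| Table 1, counted from last dose (assumption) | 0 to 7 | 28 − 7 = 21, up to 28 − 0 = 28 |
| Table 1, counted from a decision to stop after a 14-day hold (assumption) | at latest 14 + 7 = 21 | 28 − 21 = 7 |
| Section 3.7.1 | about 28 | about 0 |

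In the second row, an EoT visit on the day of the decision itself would leave 28 − 14 = 14 days, so 7 is the low end. The 2-week limit concerns delays between cycles. I found no limit on a hold inside a cycle; after a hold of 21 days or more, a visit at the end of the window would fall on day 21 + 7 = 28 or later, and the gap would be gone.

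**Step 3: who is affected.** For a patient whose last dose was *d* days before the trigger, open days = max(0, 28 − *d*). This is zero once *d* reaches 28, so only patients who stopped in the 28 days before the trigger are touched. The documents give no basis for estimating how many of the roughly 32 that would be.

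**Step 4: would tying the trigger to the follow-up visit be enough?** That visit may validly take place on day 25, which leaves 28 − 25 = 3 days open. A trigger on the completed visit alone narrows the gap but does not close it.

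**The case against.** The strongest reply is that the trigger is a minimum condition and not a data cut-off. Reporting through 28 days is mandatory under section 5.2, the TEAE definition already includes those days, and section 6.3 defers data handling to a separate SAP that ranks above the protocol text and is not in the document reviewed here. A sensible team might simply wait. This stands as a limit: the plan permits an early analysis and does not prescribe one. But nothing in the text supplied requires the wait.

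It is also fair that Table 1 names no anchor for its 7 days, so 21 to 28 open days is conditional. The conflict with section 3.7.1 is shown only for Stage 1, because section 3.7.2 has no such sentence. The trigger gap under Table 1 applies to both stages.

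A reader might infer two stronger things that the documents do not support.

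- *The primary endpoint is compromised.* It is not. Dose-limiting toxicities are assessed in Cycle 1, Days 1 to 28, and the final analysis waits until every patient is off treatment.
- *Progression-free survival is biased.* EoT carries the last MRI marked in Table 1, and section 6.3.4 says: "Analyses of tumor-related endpoints will include all evaluable data collected until initiation of subsequent anti-cancer therapy". A later scan might therefore seem likely to be lost to new therapy. But a patient whose progression was already documented at a scheduled scan has a fixed event date, whatever the EoT timing. Disease status is also followed every 8 weeks after treatment, and section 6.3.4 offers exclusion of data after EoT only as an optional sensitivity analysis. Setting the visit gap against the 5.3-month historical figure in section 3.2 would give a scale for one visit, not an effect on this trial's estimate. That scenario also needs the section 3.7.1 timing, while the safety gap needs Table 1, so the two cannot be added together.

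**Conclusion.** The point holds in a limited form. The EoT visit has two incompatible timings in current text. Under the Table 1 timing, the stated trigger can be met before the plan's own 28-day safety window has closed.

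The open period for the last patient to stop is 21 to 28 days if the Table 1 window runs from last dose, which is the natural reading but an assumption. It is about 7 days if the window runs from a decision to stop after a 2-week hold. Under section 3.7.1 it is about zero.

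What is at risk is secondary safety data (late TEAEs, SAEs and concomitant medications) in the last patient or few to stop. The conclusion assumes that the trigger is applied as written and that no later cut-off is set elsewhere. It is worth correcting because safety is the primary objective and the correction is cheap.

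**What to change.** 1. Reconcile section 3.7.1 with Table 1, the synopsis and sections 4.6.12 and 4.8, so that the EoT visit has one timing and the day it is counted from is stated.
2. In section 6.3.2 and the synopsis, replace the trigger with three conditions: all patients have discontinued treatment; at least 28 days have passed since the last patient's last dose; and each Short-Term Follow-up Visit is completed or its window has passed. The second condition closes the 3 days that a visit on day 25 would leave open.
3. Carry the same trigger into the separate SAP, since section 6.3 ranks it above the protocol text.

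The cost is wording and a later data cut. Against an EoT visit on day 0, waiting to the end of the follow-up window on day 31 moves the cut by 31 days; against day 7 it is 31 − 7 = 24 days. That is about four weeks at most. No visit, test or patient is added.

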Protocol Number: NVGN-0084-201 Version: Amendment 4 IND Number: 112,608

Dose-Escalation Rules

Dose-escalation will occur in Stage 1:

The initial dose (Dose Level 0) for QD MTD determination in will be 60 mg. Dose levels will increase in 15 mg steps:

- The dose-escalation portion of the study (Stage 1) will use a "3 + 3" design to assess the safety, tolerability, and PK of GDC 0084 administered orally in 28-day cycles:
- Each dose cohort will initially enroll 3 patients. If none of these patients experiences a DLT within the DLT assessment period (Day 1 - 28), escalation will proceed to the next higher dose level by opening the next higher dose cohort with newly recruited patients;
- If 1 patient experiences a DLT, the cohort will be expanded until a second patient experiences a DLT or to a maximum of 6 patients. When a second patient has a DLT, the MTD is determined as 1 dose level below the current dose level; i.e. the highest dose level at which less than 1/3 of patients (e.g. 1 of 6) experiences a DLT will be declared the MTD.
- If 2 or more patients experience a DLT at Dose Level 0, the MTD will be declared at 45 mg, which was the MTD established in the previous phase I study in patients with advanced glioma with a QD dosing schedule.

On the basis of the review of real-time safety data and available preliminary PK data from this study with GDC-0084, dose-escalation may be halted or modified by the sponsor as deemed appropriate.

Decisions regarding dose-escalation and selection will be made by a CRC including the medical monitor, recruiting Investigators, sponsor representative and any other relevant and necessary expert on as needs basis, according to the CRC charter.

Definition of Dose Limiting Toxicity

All AEs, including DLTs, will be reported, with severity assessed according to National Cancer Institute (NCI) Common Terminology Criteria for Adverse Events (CTCAE), version 4.03. In case a patient experiences one of the below, study participation will be terminated for this patient and the EoT visit should be performed.

For dose-escalation purposes, DLT assessments will be performed by the sponsor in consultation with the Investigators during the CRC meetings.

A DLT is defined as any one of the following toxicities occurring within the DLT assessment window (Cycle 1, Days 1 - 28) and assessed by the Investigator to be probably or possibly related to GDC-0084:

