Protocol Number: NVGN-0084-201 IND Number: 112.608

Determination of Recommended Phase 2 Dose 3.7.3

The RP2D expected to be established during this study is planned to be a dose of GDC-0084 that is both safe and tolerated, and that yields a higher exposure which would include C_{max} and AUC compared to the results of the previous phase 1 study on a QD regimen.

The RP2D will be confirmed by the CRC after completion of dose escalation.

Methods: Patients, Interventions, and Outcomes

4.1 **Study Setting**

The study will be conducted at approximately 5-7 clinical sites in the US. A list of sites will be maintained in the Trial Master File (TMF).

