4.5 Endpoints

4.5.1 **Primary Endpoint**

The primary endpoint of this study is safety-related and is the occurrence of DLTs during the study.

Protocol Number: NVGN-0084-201

Secondary Endpoints 4.5.2

Secondary endpoints are related to both, safety and clinical benefit as listed below.

Secondary Safety Endpoints:

- Treatment-emergent AEs (TEAEs), Grade 3-5 TEAEs, serious adverse events (SAEs), fatal AEs, and TEAEs leading to GDC 0084 discontinuation or study withdrawal;
- Treatment-emergent Grade 3/4 clinical laboratory abnormalities;
- Changes and shifts from baseline in clinical laboratory, vital signs, and ECG parameters;
- Change from baseline in corticosteroid use;
- Change from baseline in LVEF;
- Change from baseline in KPS;
- Concomitant medication use;
- Adherence to the dosing regimen.

Secondary Endpoints of Clinical Benefit:

- PFS measured from first dose in the dose-escalation portion (Stage 1) or from randomization in the cohort expansion portion of the study (Stage 2) to disease progression (RANO criteria) or death due to any cause:
- OS measured from first dose in the dose-escalation portion (Stage 1) or from randomization in the cohort expansion portion of the study (Stage 2) to death due to any cause;
- TTP measured from first dose in the dose-escalation portion (Stage 1) or from randomization in the cohort expansion portion of the study (Stage 2) to date of earliest disease progression according to RANO criteria.

4.5.3 **Exploratory Endpoints**

Exploratory endpoints in this study are:

- PFS measured from first dose in the dose-escalation portion (Stage 1) or from randomization in the cohort expansion portion of the study (Stage 2) to disease progression (modified RANO criteria) or death due to any cause:
- PK parameters including area under the curve from time 0 to last measurable time point (AUC_{0-last}) and/or area under the curve from time 0 to infinity (AUC_{0-inf}), maximum concentration (C_{max}), minimum concentration (C_{min}), time to reach C_{max} (T_{max}), t_{1/2}, apparent total clearance of the drug from plasma after oral administration (CL/F), and accumulation ratio for C_{max} and AUC (fed and fasted);
- Change in FDG-PET uptake in tumor and normal brain tissue (defined as normal brain tissue with similar cell type to tissue surrounding tumor) in response to GDC-0084 in patients with measurable disease:

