7.1 Cohort Review Committee

On the basis of the review of real-time safety data and available preliminary PK data from this study with GDC-0084, dose-escalation may be halted or modified by Kazia Therapeutics Limited as deemed appropriate.

Decisions regarding dose-escalation and selection will be made by a CRC including the medical monitor, recruiting Investigators, sponsor representative and any other relevant and necessary expert on as needs basis, according to the CRC charter. For dose-escalation purposes, and selection of appropriate dose levels and schedules DLT assessments and other safety/PK will be reviewed by Kazia Therapeutics Limited in consultation with the Investigators during CRC meetings.

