7.2 Interim Analysis and/or Stopping Guidelines

A description of planned analyses is shown in Section 6. There is no interim analysis planned for early efficacy or futility/early stopping. Guidelines for discontinuing the study are given in Section 4.11.

Version: Amendment 4 Date: 31 Mar 2020

Protocol Number: NVGN-0084-201

IND Number: 112.608

7.3 **Clinical Monitoring**

The study will be monitored by a CRO. Its representatives will be allowed access to all information resulting from this study and Kazia Therapeutics Limited will have an unrestricted right to use such information. The study monitor will have access to laboratory test reports and other patient records needed to verify the entries on the CRF. The patients' confidentiality will be respected as required by local law.

The sponsor and the CRO are responsible for ensuring the proper conduct of the study with regards to protocol adherence and validity of the data recorded on the CRFs. Therefore, a clinical monitor is assigned to the study. With duties to aid the Investigator and at the same time, the CRO, in the maintenance of complete, legible, organized and easily retrievable data. In addition, a clinical monitor will explain, interpret and ensure the Investigator's understanding of all applicable regulations concerning the clinical evaluation of the investigational product and ensure an understanding of the protocol, reporting responsibilities and the validity of the data.

Details on data collection and monitoring activities can be found in the study's Monitoring Plan.

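### Stage 2 enrols about 20 patients at a dose that may rest on 0/3 study patients, and the protocol schedules no DLT review with a count until all of them have finished or left Cycle 1

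*Combined protocol and SAP*

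**What the plan says.** **How the dose is chosen.** Section 3.7.1 starts each level with three patients. A level with no DLT is left for the next one, and one DLT expands the level to at most six. "When a second patient has a DLT, the MTD is determined as 1 dose level below the current dose level". No rule returns to the lower level to treat more patients there. Two or more DLTs at 60 mg send the dose back to 45 mg, the phase 1 MTD.

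**When Stage 2 starts.** Section 3.7.2 says of the expansion: "It will be initiated with recruitment of new patients as soon as the MTD for QD dosing has been determined". It enrols about 20 new patients.

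**What is reviewed, and when.**
- Section 6.3.2: "Regular cohort safety reviews will be performed as described above during Stage 1 to support dose-escalation". It lists no Stage 2 look before the final analysis.
- The synopsis adds one interim analysis that includes safety, timed thus: "After all patients in Stage 2 have completed one cycle of treatment or discontinued treatment".
- Section 7.1 gives the CRC dose escalation and "selection of appropriate dose levels and schedules DLT assessments and other safety/PK will be reviewed". Section 3.7.3 adds: "The RP2D will be confirmed by the CRC after completion of dose escalation". Neither gives it a task during Stage 2.
- Section 7.2: "Guidelines for discontinuing the study are given in Section 4.11". Section 4.11.4 allows termination for drug safety problems or at the sponsor's discretion, with no DLT count.

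**What is counted.** Section 4.5.1: "The primary endpoint of this study is safety-related and is the occurrence of DLTs during the study". The Duration of Therapy section, by contrast, lists DLTs as a reason to stop treatment only for Stage 1, Cycle 1. Section 6.3.5 tabulates several DLT components (glucose and platelets by grade, QTc, LVEF) but no DLT rate.

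**The concern.** Safety is the primary objective and DLTs are the primary endpoint. The starting dose of 60 mg is already above the phase 1 MTD of 45 mg. The Risk/Benefit Analysis reports two DLTs at 65 mg in that study and justifies 60 mg by expecting a healthier population to tolerate more. The expansion is the first real test of that expectation.

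Not expanding a 0/3 level is a common 3+3 variant and is not the issue. The issue is what follows. If the chosen dose is too toxic, the first scheduled look at accumulated Stage 2 safety comes when all of about 20 patients have had their Cycle 1 exposure. It is then too late to protect any of them during the DLT window.

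**Working it through.** **1. The plan's own figures.** Section 6.4: 12 + 20 = 32, with range 6 + 20 = 26 to 24 + 20 = 44. These reproduce. The Stage 1 minimum of 6 is matched by 0/3 at 60 mg followed by two or more DLTs in three patients at 75 mg, which makes 60 mg the MTD on 0/3. The plan states no alpha, power or target DLT rate for Stage 2.

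**2. How much 0/3 says.** Exact (Clopper-Pearson) 95% intervals:
- 0/3: 0 to 71%.
- 1/6: 0.4 to 64%.
- 1/8: 0.3 to 53%. This is 45 mg in phase 1, assuming exactly eight were treated. Section 3.5 gives exposure for 7 of 8 patients and the Risk/Benefit Analysis lists one DLT.
- A pooled 3/23, for comparison: 3 to 34%.

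The chance of 0/3 is (1−p)³: 30% at p = 1/3, 22% at 40% and 12.5% at 50%.

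**3. How often the Stage 2 dose rests on 0/3.** The documents give no DLT rates for this population, so curves are assumed. At a level with true rate p:
- cleared on 0/3: (1−p)³
- cleared on 1/6: 3p(1−p)⁵
- otherwise the MTD is one level lower.

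Example, curve E at 60 mg: 0.6³ = 0.216 and 3 × 0.4 × 0.6⁵ = 0.093. So 60 mg is cleared with probability 0.309, and 45 mg is chosen with probability 0.691. Every level on this curve exceeds 1/3, so all 30.9% of trials with an MTD of 60 mg or more are too toxic.

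Percentages of all trials, rules applied mechanically:

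| Curve (true DLT rate from 60 mg up, 15 mg steps) | 45 mg | MTD on 0/3 | MTD on 1/6 | MTD ≥ 60 mg with true rate ≥ 1/3 |
|---|---|---|---|---|
| A: .10 .20 .30 .45 .60 | 9.4 | 66.9 | 23.7 | 7.4 |
| B: .15 .25 .40 .55 .70 | 18.6 | 58.9 | 22.4 | 15.1 |
| C: .20 .35 .50 .65 .80 | 29.1 | 50.5 | 20.3 | 28.1 |
| D: .25 .45 .60 .75 .90 | 40.0 | 42.4 | 17.6 | 14.1 |
| E: .40 .55 .70 .80 | 69.1 | 21.8 | 9.1 | 30.9 |

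**4. Exposure without a review.** Expected DLTs in 20 patients are 20p: 6.7 at 1/3, 8 at 40% and 10 at 50%.

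**5. A boundary from the protocol's own limit.** Section 3.7.1 requires an observed rate below 1/3. The first Stage 2 counts at which the pooled rate is no longer below 1/3 are the same for both Stage 1 results:

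| Stage 2 DLTs | Pooled with 0/3 | Pooled with 1/6 |
|---|---|---|
| 3/5 | 3/8 = 37.5% (one fewer: 25.0%) | 4/11 = 36.4% (27.3%) |
| 5/10 | 5/13 = 38.5% (30.8%) | 6/16 = 37.5% (31.3%) |
| 6/15 | 6/18 = 33.3% (27.8%) | 7/21 = 33.3% (28.6%) |

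**6. How that boundary behaves** (exact binomial over the three looks):

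| True rate | .10 | .15 | .20 | .25 | .30 | 1/3 | .40 | .50 |
|---|---|---|---|---|---|---|---|---|
| Enrolment held, % | 1.1 | 4.0 | 10.3 | 20.5 | 34.2 | 44.4 | 64.7 | 87.2 |

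On curves A to D, holds at doses of 60 mg or more with a true rate below 1/3 occur in 11.9, 8.2, 4.4 and 9.4% of all trials. Holds at a true rate of 1/3 or more occur in 5.9, 10.3, 15.8 and 11.1%.

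Suppose a hold ended accrual with 0 to 4 further patients already entered (an assumption). At 40%, mean Stage 2 enrolment would then be 12.9 to 15.5 instead of 20, so 5.2 to 6.2 DLTs instead of 8. If the CRC resumes enrolment, the saving is smaller.

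**The case against.** **Stage 2 is not unobserved.** It is open-label. SAEs are reported within 24 hours (5.12.1) and the sponsor runs ongoing safety reviews (5.1). Continuing a patient after a DLT needs the medical monitor's agreement (3.7.1, 4.9.2), and the study can be terminated for drug safety problems (4.11.4). All of this stands, so a reader who infers that Stage 2 has no safety oversight goes too far. What is missing is a scheduled look at the cumulative count during accrual.

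**Stage 2 DLTs probably do count.** A reader might infer from the Duration of Therapy wording that they do not, which would leave the primary endpoint known from only 3 or 6 study patients at the chosen dose. The documents do not support that. The endpoint carries no stage limit in the synopsis or in 4.5.1, and the definition in 3.7.1 and the removal criteria in 4.11.2 refer to Cycle 1 without restricting the stage. The Duration of Therapy entry is a treatment-stopping criterion, not an endpoint definition. It conflicts and should be aligned, but no more than that.

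**The rules need not be mechanical.** The synopsis sets three as a minimum per cohort, the sponsor may modify escalation, and the CRC confirms the RP2D. This stands, and it is why the 0/3 frequencies are illustrations.

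**The boundary is imperfect.** On curve A unneeded holds (12%) outnumber needed ones (6%), and at a true rate of 40% it misses 35%. This stands too. A hold is a pause for a decision, not a stop.

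**The detail may sit elsewhere.** The CRC charter and the separate SAP, which Section 6.3 ranks above the protocol's statistical text, are not available here and may contain it.

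**Conclusion.** The point holds as a cheap improvement to the design. As written, the protocol schedules no DLT review with a count while about 20 patients accrue at a dose that may rest on 0/3 study patients or, at 45 mg, on phase 1 data in progressive or recurrent glioma.

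Over assumed 60 mg DLT rates of 10% to 40%, the Stage 2 dose rests on 0/3 in about 22% to 67% of trials. An MTD of 60 mg or more has a true rate of 1/3 or more in about 7% to 31%. Both ranges depend on the assumed curves and on mechanical use of the rules. They should not be read as bounds, nor as evidence that the Stage 1 design is faulty.

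Confidence is medium, because the charter or SAP may already close the gap.

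**What to change.** 1. **Sections 3.7.2 and 7.1.** Have the CRC review cumulative Cycle 1 DLTs, both arms together, after about 5, 10 and 15 Stage 2 patients have completed Cycle 1. Hold new enrolment pending its decision when the rate, pooled with Stage 1 patients at that dose, is no longer below 1/3: for example 3/5, 5/10 or 6/15. The arms can be counted together because, under 4.4.1, dosing differs on only one of the 28 days of Cycle 1. At 45 mg, where there are no Stage 1 patients to pool, the same counts can serve by convention; they hold enrolment in 2% of trials if the true rate is 12.5%. The exact boundary is the sponsor's choice.
2. **Duration of Therapy.** Align the DLT entry with 4.5.1, so that DLTs are plainly assessed by the same definition in Cycle 1 of both stages.
3. **Section 6.3.5.** Report the DLT rate at the Stage 2 dose, pooled over Stage 1 patients at that level and both Stage 2 arms, and by arm, with an exact 95% interval. Section 6.3.3 currently foresees pooling Stage 1 with fasted patients only.
4. If the CRC charter or SAP already provides this, cross-refer to it.

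**Cost.** Amendment wording, three CRC calls and one table, with no extra patients or tests and no routine wait between groups. The price is a pause in about 4%, 10%, 20% and 34% of trials at true rates of 15%, 20%, 25% and 30%, all below the protocol's limit.
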